### Statistical analysis

Means and standard deviations of participant demographic data, as well as pain, functional, and other outcome data will be calculated. Proportions and 95% confidence intervals will be calculated for categorical data.

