### Objectives:

To assess changes in pain, physical function, and health-related quality of life in patients with post-amputation neuroma-associated residual limb pain after cooled radiofrequency ablation.

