## **Procedures:**

Screening Visit: As participants are identified by the PI or CO-I's as being possible candidates for this study they will be invited to participate. Main inclusion requirement, as listed in inclusion criteria, is that the patient is being scheduled for residual limb neuroma radiofrequency ablation (RFA) procedure as standard of care. If patient states interest in the study and wishes to discuss in more detail a research coordinator will discuss at time of appointment or call and answer any questions at a time convenient to the patient. If patient is interested, and does meet inclusion/exclusion criteria, and does not have time to do the baseline questions at time of appointment a qualified research staff member will call the patient to complete by phone. It is anticipated that most subjects in this study will be identified mainly through the regular flow of the University of Utah clinics. The informed Consent process will occur either at the time the subject is in clinic or the participant may elect to complete the process at a later time. Eligibility is determined by the inclusion and exclusion criteria. Qualifying volunteers will be asked to provide both written and verbal informed consent once a standard of care treatment plan has been agreed upon by the patient and treating physician.

Baseline: Participants who meet inclusion and exclusion criteria will be enrolled into the study after consenting to participate and before receiving residual limb neuroma RFA. This procedure is considered standard of care and are typically based on physician preference. Baseline data will be collected within 2 weeks prior to the scheduled procedure, this will include information from their examination and baseline questionnaires which include the following:

An electronic data collection system (REDCap via computer) will be used to record all pre-procedure and follow-up data as listed above (See attached PDF for baseline survey)

1. Age (years).
2. Sex
3. Height (cm).
4. Weight (Kg).
5. Duration of pain (weeks).
6. Date of amputation
7. Etiology of amputation
8. Level of amputation
9. Radiologic diagnosis based on ultrasound of residual limb.
10. Patient-Reported Outcomes Measurement Information System (PROMIS) 10
11. Analgesic medication log: dose and frequency of each medication
12. Brief Pain Inventory (BPI) with modification to include numerical rating scale (NRS) score (worst, least, average, current).

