13. Groningen Activity Restriction Scale (GARS)
14. Pinprick Sensory Threshold (Von Frey Hair testing at the neuroma site)
15. Pressure Pain Threshold (algometer testing at the neuroma site)

Additional questions for post procedure survey

16. Patient Global Impression of Change (PGIC)

Patient satisfaction score (five-point Likert scale: 1, very dissatisfied; 2, dissatisfied; 3, neither satisfied nor dissatisfied; 4, satisfied; and 5, very satisfied)

Immediately after ablation the following will be obtained:

17. Post-injection Numeric Rating Scale (NRS) pain score

18. Adverse events, if they occurred

Questionnaires will be administered and collected from the participant through the University of Utah approved survey system of REDCap.

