**SOC Cooled Radiofrequency ablation (C-RFA) of Residual Limb Neuroma Procedure:**

*C-RFA:*

Our RFA procedures will be performed similar to methods described by Zhang et. al and Kim et. al with modification accounting for appropriate C-RFA technique. This technique is currently standard clinical practice at University of Utah outpatient clinic sites. During the C-RFA procedure, the participant will be positioned prone. The participant's skin will be prepared with chloroprep. An ultrasound probe will be placed on the participants' residual limb at a transverse angle in order to view the nerve and associated neuroma in long-axis. The probe will be advanced to the site of the stump neuroma. An 18-gauge C-RFA electrode with a 4mm active tip (Coolief® Cooled Radiofrequency Kit, Avanos Health Inc, Alpharetta, GA) will be placed adjacent to the neuroma. This needle will be connected via wire to a cooled radiofrequency generator. Motor testing will be performed (2.0 V, 2Hz). Sensory testing will be performed (1.0 V, 50Hz) to reproduce or exacerbate the RLP and / or PLP. At the site of the neuroma, 2 mL of local anesthetic will be injected through the needle (without triamcinolone as used per Zhang study). When the local anesthetic demonstrates pain relief, the needle will be placed into the nerve. C-RFA lesions will be created by using the typical C-RFA protocol with lesions performed for 165 seconds, with the RFA generator temperature set to 60°C (intralesional temperature >80 degrees). Once the procedure is completed, the needle will be removed. Following ablation, 0.5 mL of 0.5% bupivacaine will be injected at the site of the ablated neuroma to provide post procedure analgesia. No corticosteroids will be injected.

Following the Standard Treatment Procedure visit, routine scheduled follow-up will occur at 1 month (+/- 1 week), 3 months (+/- 2 weeks), 6 months (+/- 2 weeks), and 12 months (+/- 2 weeks) at which times all follow-up measures will be obtained. These questions will be administered over the phone or be sent to you using a secure REDCap survey by email. If received by email it will be in the form of two e-mail links in which you will again be asked questions regarding your pain level, changes in activity limitations, symptoms, emotions and

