### **Data Analysis Plan**

A categorical responder analysis will also be performed using >50% pain relief in PLP and RLP, as well as the minimally clinically important change (MCIC) for secondary outcome measures for which an MCIC has been defined, and >30% improvement for secondary outcome measures for which an MCIC has not yet been defined.

While there is no standard residual limb pain outcome recommendation, the NIH's recommendation on pain interventions was applied to this study. These secondary outcomes include PGIC score less than 3 (indicating "improved" or "very much improved"), a 6.8 or greater point reduction on the MQS III score (equivalent to approximately 10 daily morphine equivalents).

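### The objective is change, but continuous outcomes get only means and SDs: no paired mean change, SD of change or confidence interval, and no main pain score, pain type or visit is fixed

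*Combined protocol and SAP*

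**What the plan says.** The Objectives section sets one aim: "To assess changes in pain, physical function, and health-related quality of life" after cooled RFA.

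The Statistical analysis section has two sentences. For continuous data: "Means and standard deviations of participant demographic data, as well as pain, functional, and other outcome data will be calculated". For the rest: "Proportions and 95% confidence intervals will be calculated for categorical data".

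The Data Analysis Plan adds within-participant change in categorical form: "A categorical responder analysis will also be performed using >50% pain relief in PLP and RLP". Secondary measures are classed by their minimally clinically important change, or by more than 30% improvement where none is defined. There are also cut-offs on the PGIC and the MQS III. Calling these measures secondary implies that pain is the main domain.

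The pain data hold several candidates for a main result. The Procedures section records a modified Brief Pain Inventory with "numerical rating scale (NRS) score (worst, least, average, current", and follow-up is at 1, 3, 6 and 12 months. The Introduction calls the study a single-arm pilot meant to inform a later randomised trial, yet states its aim as defining an effect attributable to cooled RFA.

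**The concern.** An objective about change in pain, function and quality of life calls for a continuous analysis of change. The plan summarises outcome values and does not mention change from baseline, its SD or an interval for its mean. Three things follow.

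- Mean change, which most readers will look for, would have no stated precision. Visit SDs cannot supply it, because the SD of change also depends on the baseline to follow-up correlation.
- If some participants are lost, the baseline mean and the follow-up mean describe different groups, and their difference is not the mean change of anyone in particular.
- With no main NRS item, pain type or visit named, the headline result could be picked with the results in view. This applies equally to the pain responder rate, whose 50% threshold is attached to no item or visit.

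**Working it through.** The plan has no figure to reproduce: it gives no SD, correlation, dropout rate or power calculation. The only trial input is n. The Sample Size section gives 20 for Utah and 10 for all centers, so both are shown. Everything else is an assumption for illustration.

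**Precision of mean change.** Assume an NRS SD of 2.0 at each visit and a baseline to follow-up correlation r.

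- SD of change = 2.0 × √(2(1 − r)) = 2.53, 2.00 and 1.26 for r = 0.2, 0.5 and 0.8.
- Paired half-width = t(0.975, n − 1) × SD of change / √n.
- Half-width from visit SDs alone, treating visits as independent = t(0.975, 2n − 2) × 2.0 × √(2/n).

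| n | visit SDs alone | paired, r = 0.2 | r = 0.5 | r = 0.8 |
|---|---|---|---|---|
| 20 | 1.28 | 1.18 | 0.94 | 0.59 |
| 10 | 1.88 | 1.81 | 1.43 | 0.90 |

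The gain from pairing is slight at r = 0.2 and more than halves the half-width at r = 0.8.

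**Dropout (hypothetical).** Suppose 20 enrol with baseline mean 6.0, 5 with baseline mean 8.0 are lost, and the 15 followed average 4.0.

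- Difference in visit means: 6.0 − 4.0 = 2.0.
- Baseline mean of the 15 followed: (20 × 6.0 − 5 × 8.0)/15 = 80/15 = 5.33.
- Mean paired fall: 5.33 − 4.0 = 1.33.
- If those lost averaged 7.0 instead: (120 − 35)/15 = 5.67, and the paired fall is 1.67.

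The gap is simply the baseline mean of everyone minus that of those followed. It vanishes with complete follow-up, or if those lost resemble the rest at baseline.

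**Freedom of choice.** Four NRS items × four visits = 16 candidate main pain results, or 32 if RLP and PLP are each scored.

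**What an SD of change would be worth.** The chi-square 95% interval for an SD runs from √((n − 1)/χ²(0.975)) to √((n − 1)/χ²(0.025)) times the estimate: 0.76 to 1.46 at n = 20 and 0.69 to 1.83 at n = 10. For an observed SD of change of 2.0, an assumed 1-point difference and 90% power, the size per arm is 2 × (1.960 + 1.282)² × SD². At the interval limits this spans 49 to 180 (n = 20) or 40 to 281 (n = 10).

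**The case against.** The best defence is that change is already analysed. The responder criteria measure improvement within each participant across pain and the secondary measures, and the Statistical analysis section puts 95% intervals on categorical data. This stands. A reader might infer from the continuous plan that the objective would be reported with no measure of precision at all; the documents do not support that. The gap is confined to mean change.

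A second defence is that this is a small descriptive pilot with no hypothesis test. It can report every item at every visit, and paired results can be computed later from stored data. This also stands in part. A reader might infer that the headline will be chosen after the fact, but that is a risk, not a certainty. Later computation recovers the estimates; it does not recover the prior commitment to one of them.

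Third, the dropout example is constructed. The plan states no dropout rate, and the first exclusion criterion removes people unable to provide 12 months of follow-up. The example shows what can happen, not an expected size.

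Fourth, the case from the later trial is weak. The ranges above settle little, and the planned visit SD can already size a trial on follow-up scores: with SD 2.0, a 1-point difference and 90% power, 2 × (1.960 + 1.282)² × 4 = 84.06, or 85 per arm, the same as for change scores at r = 0.5. The argument for the fix should rest on the objective, not on sizing the trial.

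**Conclusion.** The point holds in limited form and should be fixed. Change is planned with precision on the categorical scale. On the continuous scale there is no mean within-participant change, SD of change or interval, and no main pain item, pain type or visit is set for either scale. The half-widths rest on an assumed SD of 2.0 and assumed correlations, and the dropout gap of 2.0 − 1.33 = 0.67 points rests on an invented pattern of loss. The omission itself is plain from the text as supplied. One caution: the Data Analysis Plan introduces the responder analysis as an addition, yet no preceding analysis appears, so the source file should be checked for a missing sentence.

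The Introduction's wording about an attributable effect is a minor matter. A reader might take it as a planned causal claim, but the same section calls the study a single-arm pilot, the formal objective speaks only of change, and no planned analysis attributes anything. It remains worth rewording: without a comparator, change may include placebo response, natural course, regression to the mean and co-medication.

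**What to change.** In Statistical analysis, add that for each continuous outcome, at each follow-up where it is collected, the report will give mean change from baseline, SD of change and a 95% CI for mean change, with the number contributing and their baseline mean. The last two items matter because the paired mean describes only those followed.

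Before data are viewed, name one main pain measure (which NRS item, and RLP or PLP) and one main visit. Keep the responder rates, and apply the same item and visit to the pain responder rate.

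State which outcomes are collected at follow-up. The baseline list includes "Pinprick Sensory Threshold (Von Frey Hair testing at the neuroma site") and "Pressure Pain Threshold (algometer testing at the neuroma site"), but of follow-up the procedure section says "These questions will be administered over the phone or be sent to you using a secure REDCap survey by email". If the thresholds are not repeated, leave them out of the change analysis.

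Minor: in the Introduction, reword the aim as *estimate within-participant change after cooled RFA in* the listed outcomes.

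The cost is a few sentences and a little more analysis, with no new data for the questionnaire outcomes. The downsides are a more modest claim and an SD of change too imprecise to guide the later trial's size more than loosely.
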